1. OBJECTIVES

1.1 Study Design

This is a prospective, pilot study.

1.2 Primary Objectives

To estimate the agreement rate of detecting metastatic disease between ¹⁸F-fluciclovine-PET/CT and histopathology from radical cystectomy for detecting locoregional metastatic disease in patients with cT2-T4N0M0 muscle invasive bladder cancer by conventional CT/MRI imaging.

1.3 Secondary Objectives

1.3.1 To estimate the rate of detection of suspected distant metastatic disease by ¹⁸F-fluciclovine -PET/CT in patients with cT2-T4N0M0 muscle invasive bladder cancer by conventional CT/MRI imaging.

1.3.2 To investigate the relationship between ¹⁸F-fluciclovine uptake on PET/CT and pathologic tumor stage and size of primary bladder tumor after radical cystectomy.

1.3.3 To investigate the relationship between ¹⁸F-fluciclovine uptake on PET/CT and the presence/absence of a ASCT2 and LAT1 amino acid transporters in the resected primary bladder tumors.

2. BACKGROUND

2.1 Urothelial carcinoma of the bladder

Urothelial carcinoma of the bladder is the fifth most common malignancy in the United States, with an estimated 75,000 new cases and 15,000 deaths in a year [1]. Approximately 25% of new cases are muscle-invasive bladder cancer (MIBC), while the rest are non-muscle-invasive bladder cancer (NMIBC). Accurate staging of bladder cancer is paramount in deciding the appropriate course of management. While NMIBC is generally managed by cystoscopic resection with intravesical BCG or chemotherapy, the standard treatment for MIBC is radical cystectomy (RC) preceded by neoadjuvant chemotherapy (NAC) in cisplatin-eligible patients [2-4]. It is estimated that ~30% of patients undergoing RC may have nodal metastases [5, 6]. Metastatic disease has exhibited improved outcomes when treated with first-line systemic cisplatin-based chemotherapy and salvage post-platinum therapy using one of multiple programmed death (PD)-1 and PD-ligand (L)-1 inhibitors (pembrolizumab, atezolizumab, durvalumab, nivolumab, avelumab) [7-13]. Additionally, pembrolizumab and atezolizumab are approved for the first-line therapy of cisplatin-ineligible patients based on durable responses [14, 15]. Therefore, pre-operative identification of those with node-positive metastatic disease will enhance prognostic risk stratification and tailoring of neoadjuvant therapy, for example with the consideration of clinical trials of more aggressive and promising neoadjuvant combination

regimens and tailoring the extent of lymph node dissection based on the extent of node-positive disease.

2.2 Current imaging methods to stage bladder cancer

Current imaging methods used to stage bladder cancer predominantly include computed tomography (CT) and magnetic resonance imaging (MRI). While both are useful in locoregional staging, both exhibit limitations. CT and MRI rely on nodal enlargement as an indicator of disease involvement. Non-enlarged lymph nodes harboring disease can be falsely negative by anatomic imaging. Conversely, false positive lymphadenopathy from benign etiologies can preclude eligible patients from RC. CT and MRI sensitivity for detection of nodal metastasis ranges from 31-50% and specificity ranges from 68-100% [6]. Some reports suggest that 40% of those with bladder confined disease by imaging have extravesical and/or pathologically node-positive disease at RC [16-20].

Fluorodeoxyglucose (¹⁸FDG)-positron emission tomography (PET) is a functional imaging modality that has excellent sensitivity for detecting metastatic disease when combined with anatomic CT or MRI [21-25]. However, effective use of FDG-PET/CT in bladder cancer is limited by the fact that FDG is excreted in urine. Saturation of the imaging signal from within the bladder and urinary tract can affect accurate assessment of locoregional FDG uptake. Furthermore, elevated FDG uptake can also be seen in benign inflammatory conditions and within the gastrointestinal tract, which can also confound staging assessment. Correspondingly, FDG-PET is not approved by regulatory agencies to stage bladder cancer [4].

Given the limitations of both conventional structural CT/MRI and FDG-PET to stage urinary tract cancers, an alternative functional imaging marker without these limitations is highly desirable and warrants investigation.

2.3 ¹⁸Fluorine-Fluciclovine

Anti-1-amino-3-F-18-fluorocyclobutane-1-carboxylic acid (FACBC or ¹⁸F-fluciclovine) is a novel radiotracer for imaging amino acid transporters, which can be over-expressed in cancer [26]. ¹⁸F-fluciclovine was recently approved by the Food and Drug Administration for the detection of biochemically recurrent prostate cancer [27, 28] and it may have a role in complementing MRI for staging localized prostate cancer [29] and radiation planning [30]. ¹⁸F-fluciclovine is predominantly transported in cells via the L-system amino acid transporters, ASCT (alanine-serine-cysteine transporters)-2 and LAT (large neutral amino acid transporters)-1, with peak uptake in tumors 5 to 20 minutes after injection.

In addition to prostate cancer, ¹⁸F-fluciclovine has been shown to accumulate in other tumor types, including breast, lung and colon cancer [31]. A unique feature of ¹⁸F-fluciclovine biodistribution is low bladder uptake at early post injection timepoints when elevated uptake in tumors is already seen [32, 33]. Additional advantages of ¹⁸F-fluciclovine over other naturally occurring amino acid PET imaging agents, such as ¹¹C methionine, include a longer radiolabel half-life (110 minutes for ¹⁸F agents vs 20 minutes for ¹¹C) such that an on-site cyclotron is not required [34]. Other ¹¹C agents have also been tested, including ¹¹C choline and ¹¹C acetate

PET/CT have been tested for staging bladder cancer with equivocal results [35].

No adverse effects to patients that is directly attributable to ¹⁸F-fluciclovine have been reported to date [36].

2.4 Rationale for staging bladder cancer with ¹⁸F-fluciclovine

Amino acid transporters are overexpressed in many cancers [26]. Diets rich in the amino acids L-isoleucine and L-leucine have been shown to promote bladder cancer in rats [37]. The LAT-1 transporter has been implicated as responsible for leucine uptake in T24 bladder cancer cells [38]. Inhibition of LAT-1 can prevent cell growth in bladder cancer cell lines [38], and overexpression of LAT-1 can predict progression of urinary tract cancer [39, 40]. These findings suggest that the amino acid transporters are a viable imaging target in bladder cancer.

¹⁸F-fluciclovine has been shown to be a promising imaging agent in multiple cancer types. The biodistribution profile of ¹⁸F-fluciclovine shown in prior studies suggests that it may be useful for imaging bladder cancer. Experiments with a rat orthotopic prostate cancer model compared the uptake of ¹⁸F-fluciclovine with that of FDG and found that target-to-background ratio was higher for ¹⁸F-fluciclovine with only minimal bladder accumulation. Compared to FDG, ¹⁸F-fluciclovine is only minimally eliminated by the kidneys during the typical imaging time course suggesting that it may be more optimal than FDG for imaging renal and urinary tract malignancies. ¹⁸F-fluciclovine is physiologically found in the pancreas, liver, bone marrow, and muscle, with negligible uptake in kidneys, bowel, and shows delayed urinary excretion even when compared with ¹¹C choline, leading to a more favorable distribution profile in the abdomen and pelvis [32].

Taken together, these studies suggested that ¹⁸F-fluciclovine-PET/CT may be a viable imaging strategy to accurately stage muscle invasive bladder cancer.

2.5 Correlative Studies Background

LAT1 and ASCT2 expression are determined by immunohistochemical (IHC) staining with anti-LAT1 and anti-ASCT2 monoclonal antibodies, respectively. Immunostaining with these antibodies are based on standard protocols and have been described in detail previously [41]. Briefly, 5 unstained slides per patient consisting of 5 μ M thick sections of formalin fixed paraffin embedded (FFPE) tissue are obtained from deparaffinized and rehydrated sections. These sections are treated with 0.3% hydrogen peroxide (H_2O_2) in methanol for 30 min to block endogenous peroxidase activity. To expose the antigens, sections are autoclaved in ethylenediaminetetraacetic acid (pH 8.0) for 5 min and cooled for 30 min. After rinsing in phosphate-buffered saline, the sections are incubated with anti-LAT1 and anti-ASCT2 antibodies overnight followed by secondary staining with horseradish peroxidase-conjugated antibodies. Visualization of staining is carried out using 0.02% 3,3'-diaminobenzidine tetrahydrochloride and 0.01% H_2O_2 in 0.05 M Tris-HCl (pH 7.4). Negative control tissue sections were stained as described above, except that the primary antibodies are omitted. The LAT1 and ASCT2 expression scores are assessed by the extent of staining as follows: 0, less than 5% of tumor area stained; 1, 5–10% stained; 2, 11–25% stained; 3, 26–50% stained; and 4, 51% or more stained.

3. PARTICIPANT SELECTION

3.1 Eligibility Criteria

Participants must meet the following criteria on screening examination to be eligible to participate in the study:

- 3.1.1 Participants must have histologically or cytologically confirmed urothelial carcinoma of the bladder.
- 3.1.2 Participants must have cT2-T4N0 disease at the time of the study, as defined by conventional CT or MRI imaging. Patients must have no definite evidence of locoregional or distant metastatic disease at the time of study eligibility, as defined by conventional imaging.
- 3.1.3 Radical cystectomy must be planned for the patient after the planned ¹⁸F-fluciclovine-PET/CT.
- 3.1.4 Patients may or may not have had prior neoadjuvant therapy prior to this study.
- 3.1.5 Age ≥ 18 years. Since no dosing or adverse event data are currently available on the use of ¹⁸F-fluciclovine in participants <18 years of age, and the majority of bladder cancer occur in the adult population [42], children are excluded from this study but will be eligible for future pediatric trials.
- 3.1.6 ECOG performance status ≤ 2 (Karnofsky $\geq 60\%$, see Appendix A)
- 3.1.7 Ability and willingness to comply with the study procedures.
- 3.1.8 The effects of ¹⁸F-fluciclovine on the developing human fetus are unknown. For this reason and because radiopharmaceuticals may be teratogenic, women of childbearing potential and men must agree to use adequate contraception (barrier method of birth control; abstinence) prior to study entry and for 24 hours after the PET/CT scan is completed. Should a woman become pregnant or suspect she is pregnant while participating in this study, she should inform her treating physician immediately.
- 3.1.9 Ability to understand and the willingness to sign a written informed consent document

3.2 Exclusion Criteria

Participants who exhibit any of the following conditions at screening will not be eligible for admission into the study:

- 3.2.1 Participants with other known malignancy that has required treatment in the past 3 years.
- 3.2.2 Pregnant women are excluded from this study because ¹⁸F-fluciclovine is a radiopharmaceutical with the potential for teratogenic effects. Because of the radiation exposure to a nursing infant from ¹⁸F-fluciclovine, women who are breastfeeding are also excluded from this study.
- 3.2.3 History of allergic reactions attributed to compounds of similar chemical or biologic composition to ¹⁸F-fluciclovine.
- 3.2.4 Uncontrolled intercurrent illness including, but not limited to, ongoing or active infection, symptomatic congestive heart failure, unstable angina pectoris, cardiac arrhythmia, or psychiatric illness/social situations that would limit compliance with study requirements.
- 3.2.5 Contraindications for PET/CT including:
 - Severe claustrophobia
- 3.2.6 Any past or current condition that in the opinion of the study investigators would confound the results of the study or pose additional risk to the patient by their participation in the study.

3.3 Inclusion of Women and Minorities

Both men and women of all races and ethnic groups are eligible for this trial.

4. REGISTRATION PROCEDURES

4.1 General Guidelines for DF/HCC Institutions

Institutions will register eligible participants in the Clinical Trials Management System (CTMS) OnCore. Registrations must occur prior to the initiation of any protocol-specific therapy or intervention. Any participant not registered to the protocol before protocol-specific therapy or intervention begins will be considered ineligible and registration will be denied.

An investigator will confirm eligibility criteria and a member of the study team will complete the protocol-specific eligibility checklist.

Following registration, participants may begin protocol-specific therapy and/or intervention. Issues that would cause treatment delays should be discussed with the Overall Principal Investigator (PI). If the subject does not receive protocol therapy following registration, the subject must be taken off-study in the CTMS (OnCore) with an appropriate date and reason entered.

4.2 Registration Process for DF/HCC Institutions

Applicable DF/HCC policy (REGIST-101) must be followed.

4.3 General Guidelines for Other Investigative Sites

N/A

4.4 Registration Process for Other Investigative Sites

N/A

5. IMAGING PLAN

5.1 Summary

All procedures will be performed on an outpatient basis. Expected toxicities and potential risks are described in Section 6 (Expected Toxicities and Dosing Delays/Dose Modification).

This is a pilot study investigating ¹⁸F-fluciclovine PET/CT for imaging patients with muscle invasive bladder cancer. The investigational imaging procedure in this study is ¹⁸F-fluciclovine-PET/CT.

After the participant meets eligibility criteria for the study and informed written consent is obtained, the participant will undergo the study procedure (¹⁸F-fluciclovine-PET/CT imaging). ¹⁸F-fluciclovine-PET/CT will be obtained within 6 weeks of the standard-of-care diagnostic staging procedures (MRI and/or diagnostic CT).

Participants will then undergo radical cystectomy per standard-of-care as determined by the medical oncologist. At the time of radical cystectomy, which usually includes pelvic lymph node dissection, standard evaluation of the surgical specimen will determine pathologic staging. We will assess the results of the standard evaluation of the surgical specimen for metastatic disease. These results will be compared with staging as determined by ¹⁸F-fluciclovine PET/CT and standard-of-care diagnostic imaging.

The participant will have completed all study requirements once tissue is obtained at radical cystectomy.

5.2 ¹⁸F-fluciclovine PET/CT imaging

5.2.1 The ¹⁸F-fluciclovine-PET/CT imaging procedure is described in Section 5.4.

Participants will be instructed to refrain from strenuous exercise for the 24 hours preceding the PET/CT exam, since amino acid transporters expression have been

noted to increase in skeletal muscle for that period after exercise [43]. Participants will be NPO for 4 hours prior to administration of ¹⁸F-fluciclovine.

5.2.2 Participants will be provided with instructions regarding what precautions to take at home once they receive the study agent. As with all radiopharmaceuticals administered, participants will receive a card stating that they have received a radiopharmaceutical for medical purposes which includes, but is not limited to, radiopharmaceutical, dosage, suggested time of detection, suggested contamination item storage duration, and institutional and departmental contact information.

Given the short half-life and diagnostic dose of ¹⁸F-fluciclovine (110 minutes), no special precautions regarding excreta or contact with other humans are necessary.

5.3 Surgery

After completion of the ¹⁸F-fluciclovine-PET/CT scan, participants will undergo standard-of-care radical cystectomy surgery as determined by medical oncology and urology. If surgical plans (for example, the presence of unsuspected extensive disease precluding cystectomy) are altered based on clinical findings during surgery, the patient may remain evaluable if a lymph node dissection is performed as determined by the study team. Results from the standard-of-care evaluation of the pathologic specimens will be collected and reviewed. This includes evaluation of pathological samples for metastatic cancer burden.

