5.5 Duration of Study Participation

Duration of study participation will be until the time that surgical specimens are obtained at the time of radical cystectomy.

Participants may be removed from study participation prior to the scheduled completion if one of the following events occurs:

- Unacceptable adverse event(s),
- Participant demonstrates an inability or unwillingness to comply with the study procedures,
- Participant decides to withdraw from the study,
- Condition that would result in confounding information for study procedure interpretation as determined by the study investigators,
- General or specific changes in the participant's condition render the participant unacceptable for continuing study procedures in the opinion of the treating investigator.

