13.3 Sample Size, Accrual Rate and Study Duration

The planned sample size is 16 participants with completed ¹⁸F-fluciclovine-PET/CT scans and pathology dissection. Patients who did not complete the scans or without pathology dissection are unevaluable and will be replaced. Considering 4 patients who may be unevaluable and replaced, up to 20 patients can be enrolled. The estimated accrual rate is 1 participant/month, and accrual is expected to complete in another 16 months. Participants who undergo ¹⁸F-fluciclovine-PET/CT but have altered surgical plans due to clinical findings during surgery may remain evaluable and not replaced if a lymph node dissection was performed as determined by the study investigators. This will not affect the primary study objective given the primary objective is the agreement rate between PET/CT and pathology for metastases. Participants who do not undergo cystectomy will not be included for secondary objectives (2 and 3).

We will employ a Simon's 2-stage design to test the hypothesis that the agreement rate of metastatic disease status between ¹⁸F-fluciclovine-PET/CT and histopathology will be 75%, compared to a null agreement rate of 50%. In the first stage we will enroll 10 patients, and if 6 or more scans among those 10 are in agreement regarding metastatic disease status, we will open the second stage of accrual to enroll an additional 6 patients, making a total sample size of 16 patients. If fewer than 6 scans are in agreement in the first stage then the study may be stopped or the study design may be amended to enroll additional patients. In order to consider the study a success, a total of 11 or more scans need to be in agreement among all 16 scans. This design has a 0.62 probability of stopping early under the null, and has 79.9% power while maintaining an overall one-sided type I error rate of 0.101. The agreement rate between ¹⁸F-fluciclovine-PET/CT and histopathology is expected to be 75% (or higher) and the corresponding 90% CI will be (0.52, 0.91).

| Accrual Targets | | | |
|---|------------|--------|-------|
| Ethnic Category | Sex/Gender | | |
| | Females | Males | Total |
| Hispanic or Latino | + | = | = |
| Not Hispanic or Latino | + | = | = |
| Ethnic Category: Total of all subjects | (A1) + | (B1) = | (C1) |
| Racial Category | | | |
| American Indian or Alaskan Native | + | = | = |
| Asian | + | = | = |
| Black or African American | + | = | = |
| Native Hawaiian or other Pacific Islander | + | = | = |

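### Sections 5.3 and 13.3 leave it to the study team, after scan and surgery, whether a patient with altered surgery is evaluable, so the stated type I error of 0.101 is not guaranteed

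*Combined protocol and SAP*

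**What the plan says.** Section 5.3 places surgery after the scan. If the plan changes because of findings during surgery (its example is unsuspected extensive disease that precludes cystectomy), "the patient may remain evaluable if a lymph node dissection is performed as determined by the study team". Section 13.3 says that such participants "may remain evaluable and not replaced if a lymph node dissection was performed as determined by the study investigators", which implies that one judged unevaluable is replaced. It adds that this does not affect the primary objective. Replacement is limited by the ceiling of 20 enrolled for 16 analysed.

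Four other sections bear on who counts:
- **13.1**, to which 13.5 refers for the primary analysis, takes every scan performed as the denominator.
- **13.2** analyses 16 patients with a completed scan and pathology dissection. Section 13.3 matches this by making patients who lack either one unevaluable and replaced.
- **13.7.2** makes patients with a scan and radical cystectomy evaluable, and does not mention those with node dissection only.
- **5.7** mentions replacement only for participants taken off study before the scan.

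Section 5.5 separately allows removal before scheduled completion for a "Condition that would result in confounding information for study procedure interpretation as determined by the study investigators".

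The decision rule is in 13.3. The study goes on "if 6 or more scans among those 10 are in agreement regarding metastatic disease status", and for success "a total of 11 or more scans need to be in agreement among all 16 scans". The stated properties are an "overall one-sided type I error rate of 0.101" and that the design "has 79.9% power".

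**The concern.** Evaluability should be fixed by facts that do not depend on whether scan and pathology agree. Here, for one subgroup, it is a judgement made once the operative findings are known. The scan has been done by then, and nothing in the documents keeps its result, or the nodal pathology, from those who decide.

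The subgroup is unlikely to be neutral. All participants are node-negative and free of definite metastases on CT or MRI at entry. If unsuspected extensive disease is found at surgery, the scan was negative and the dissected nodes are positive, the patient is a discordant case. Leaving that patient out and enrolling another removes a disagreement from a total of 16 in which 11 agreements mean success. The assurance in 13.3 concerns keeping such patients. It does not address leaving them out selectively.

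**Working it through.** **Inputs (all Section 13.3).** Null agreement p0 = 0.50, alternative 0.75; first stage 10 patients, continue with 6 or more agreements; final 16 patients, success with 11 or more; replacements at most 20 − 16 = 4.

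**Step 1: reproduce the stated figures.** P(success) = Σ over x = 6 to 10 of P(Bin(10, p) = x) × P(Bin(6, p) ≥ 11 − x). At p = 0.50:

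| x | P(x of 10) | P(≥ 11 − x of 6) | product |
|---|---|---|---|
| 6 | 0.20508 | 0.10938 | 0.02243 |
| 7 | 0.11719 | 0.34375 | 0.04028 |
| 8 | 0.04395 | 0.65625 | 0.02884 |
| 9 | 0.00977 | 0.89062 | 0.00870 |
| 10 | 0.00098 | 0.98438 | 0.00096 |

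The sum is 0.1012. The same sum at p = 0.75 is 0.79995, and P(Bin(10, 0.50) ≤ 5) = 0.623. These match the stated 0.101, 79.9% and 0.62.

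**Step 2: allow selective replacement.** Let V(e, c, r) be the probability of success with e evaluable patients so far, c agreements and r replacements left. Let f be the share of discordant cases that are dropped and replaced.

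- V = 0 if e = 10 and c < 6. At e = 16, V = 1 if c ≥ 11 and 0 otherwise.
- For r > 0: V(e, c, r) = p·V(e+1, c+1, r) + (1 − p)·[f·V(e, c, r−1) + (1 − f)·V(e+1, c, r)].
- For r = 0: V(e, c, 0) = p·V(e+1, c+1, 0) + (1 − p)·V(e+1, c, 0).

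The type I error is V(0, 0, R) at p = 0.50, with R the maximum number of replacements.

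*Upper limits, f = 100%:*

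| R | 0 | 1 | 2 | 3 | 4 |
|---|---|---|---|---|---|
| type I error | 0.101 | 0.163 | 0.237 | 0.321 | 0.410 |

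*Milder assumptions, R = 4:*

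| f | 5% | 10% | 20% | 30% |
|---|---|---|---|---|
| type I error | 0.121 | 0.144 | 0.199 | 0.263 |

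The documents give no rate of altered surgery, so f is an assumption. At the null half of all patients are discordant, so f = 5% or 10% means that 2.5% or 5% of scanned patients are discordant and dropped.

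**Step 3: other directions.** If patients are dropped without regard to agreement (10%, 20% or 50% of them, up to four replacements), the error stays at 0.1012. If 10% of concordant cases are dropped instead, it falls to 0.069.

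**Step 4: set the rules side by side.** Take a patient with a completed scan, abandoned cystectomy and a node dissection. Under 13.1 the scan is in the denominator. Under 13.2 the patient qualifies. Section 13.7.2 covers only patients who had cystectomy, so it does not make this patient evaluable. Under 5.3 and 13.3 the patient *may* count. Section 5.7 foresees no replacement after the scan, whereas 13.3 does. No section takes precedence, so discretion decides.

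**The case against.** The strongest reply is that the discretion is narrow. It covers only patients whose plans change during surgery and who have a node dissection. A patient with a scan and a completed cystectomy is evaluable under 13.7.2, so an ordinary discordant case cannot be dropped by this clause. Reaching 0.410 through it would need four discordant altered-surgery patients among 20; if such patients were 5% of those enrolled, the chance of four or more is about 1.6%. This stands, and the figures of 0.163 and above in the first table must be read as limits. A reader might infer that any scanned patient can be dropped, or that 0.410 is the error to expect; the documents support neither.

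Altered surgery is also not the same as a missed lesion. A positive scan with positive nodes agrees, and so does a negative scan with extensive local disease and negative nodes. The clause makes those patients optional too. This also stands: the subgroup may be enriched for discordance, but that is plausible rather than shown.

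The phrase about the team's determination could mean only confirming that a dissection took place. That reading is possible, but dissection is a recorded fact, and *may* would remain permissive. That the team knows the scan result is inferred from the sequence and the absence of any blinding; it is not stated.

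A reader might also treat Section 5.5 as a second way to drop discordant cases. The documents do not support that. Removal there precedes the surgical specimens, so agreement is not yet known, and the calculation above does not apply. That such a patient would be replaced is an inference from 13.3 which sits badly with 5.7.

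Finally, this is a pilot whose objective is to estimate agreement, with a 90% exact interval. That limits the weight of the point. However, 13.3 also sets a hypothesis test and a success threshold, and selective exclusion would bias the estimate as well.

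**Conclusion.** The point holds in a limited form. For patients with altered surgery and a node dissection, the plan makes entry to the primary analysis a judgement after scan and surgery, with no criterion and no blinding described, and its other evaluability rules conflict. The stated error of 0.101 is correct for the design as written but is not guaranteed under this rule. One selectively replaced discordant case can raise it to 0.163. With an assumed 5% or 10% of discordant cases dropped it is about 0.121 or 0.144, and the ceiling with all four replacements is 0.410.

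It would go too far to say that 0.101 no longer holds: it fails only if the choice is related to agreement, and the documents do not show that it would be. The sizes rest on assumed values of f, on independent patients, and on a null agreement rate of 50%. With 16 patients and a repair this cheap, the sponsor should make the change.

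**What to change.** 1. In 5.3 and 13.3, replace the permissive clause with: *is evaluable if the PET/CT was completed and lymph node histopathology is available, whether or not cystectomy was completed*.
2. Align 5.7, 13.1, 13.2 and 13.7.2 with that one rule, including the denominator and when replacement is allowed.
3. State in 5.5 that removal after the scan for a confounding condition does not by itself exclude from the primary analysis a patient who has a scan and nodal pathology.
4. Report every scanned patient who is replaced, with the reason and the scan result. Add a sensitivity analysis of the agreement rate that includes them, for example counted as discordant.

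Item 4 is needed because item 1 still leaves out patients whose surgery is abandoned without node dissection, and that exclusion may also be related to outcome.

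The cost is wording in six sections and one extra analysis, with no added patients or procedures. The downside is small: a few patients with limited dissection or a confounding condition stay in the primary analysis.
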